8.0 DISCONTINUATION CRITERIA

8.1 Discontinuation of Study Treatment

In considering discontinuation of the study treatment, the Investigator should give particular consideration of the following:

Liver Test Abnormalities

The following monitoring schedule is proposed when a case of acute liver function abnormalities or worsening of a liver function abnormality is reported:

- 1) If ALT or AST increases to $>3 \times$ ULN but $<5 \times$ ULN, in participants with normal transaminases at baseline, repeat testing within 48 to 72 hours including ALT, AST, ALP and Total Bilirubin [TB], should be performed and query for symptoms made. If repeat testing shows ALT or AST persists $>3 \times$ ULN (alternatively 2-fold increase above baseline for participants with abnormal values before study drug exposure), close observation is to be initiated as follows:
 - Regular monitoring (twice to three times a week) is required (AST, ALT, ALP and TB)
 - Initiate potential DILI evaluation for alternative etiologies. Testing for alternative etiologies can include serology tests (hepatitis A, hepatitis B, hepatitis C, Cytomegalovirus (CMV), Epstein-Barr Virus (EBV), Herpes Simplex Virus (HSV), varicella zoster virus (VZV), parvovirus, toxoplasmosis), imaging, and pathology assessments (creatinine phosphokinase, clotting) as appropriate to the clinical situation. Consider a hepatology consult.
 - Follow the patient, if laboratory parameters stabilize or normalize the patient can continue on study treatment during this period.

If the increase in ALT or AST to $> 3 \times$ ULN is also in association with abnormalities in TB or INR or with clinical hepatitis as specified below, study drug **MUST** be stopped.

- 2) If AST or ALT are $\geq 5 \times$ ULN, a repeat value should be obtained within 24-48 hours. If the repeat ALT OR AST values is $\geq 5 \times$ ULN, the drug should be discontinued and the patient followed until the laboratory values normalize or stabilize, in addition to initiating potential (Drug Induced Liver Injury) DILI evaluation.
- 3) When the following abnormal liver test conditions are met, study treatment **MUST** be discontinued, the study PI be informed, and further steps discussed:
 - ALT or AST $>3 \times$ ULN and total bilirubin $>2 \times$ ULN **OR**
 - ALT or AST $>3 \times$ ULN and international normalized ratio (INR) >1.5 **OR**

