- Any elevation in ALT or AST with clinical hepatitis: ALT or AST >ULN and the appearance of worsening fatigue, nausea, vomiting, right upper quadrant pain/tenderness, fever, rash, or eosinophilia
- Alkaline phosphatase >2x ULN and direct bilirubin >2 x ULN

4) When the following hepatic adverse events are met, study treatment **MUST** be discontinued, the study PI be informed, and further steps discussed:

- Regardless of the magnitude of the transaminase elevation, if the bilirubin is elevated (any level) in addition to the presence of signs and symptom(s) such as rash, eosinophilia, nausea, vomiting, or right upper quadrant pain
- INR ≥ 1.5 (unless due to therapeutic anti-coagulant use) and TB ≥ 2.5 x ULN, irrespective of the magnitude of ALT or AST elevation
- TB elevation ≥ 2.5 x ULN, and ALP ≥ 2.5 x ULN for cholestatic liver injury.

For each scenario, initiate potential DILI evaluation for alternative etiologies and consider a hepatology consult. Liver biopsy should be considered for DILI. The complete liver profile including PT/INR must be repeated within 48-72 hours after first abnormal value is obtained. Follow the patient until laboratory parameters stabilize or normalize. Study medication can be restarted only if an alternative etiology is “definitively” identified and liver tests have returned to baseline. Testing for alternative etiologies can include serology tests (hepatitis A, hepatitis B, hepatitis C, Cytomegalovirus (CMV), Epstein-Barr Virus (EBV), Herpes Simplex Virus (HSV), varicella zoster virus (VZV), parvovirus, toxoplasmosis), imaging, and pathology assessments (creatinine phosphokinase, clotting) as appropriate to the clinical situation.

Clinically significant liver function abnormalities should be reported as an AE/AESI.

EKG Abnormalities

If a clinically significant finding is identified (including but not limited to changes from baseline in QTcF after enrolment), the Investigator or qualified designee will determine if the participant can continue in the study and if any change in participant management is needed. This review of the EKG printed at the time of collection must be documented. Any new clinically relevant finding should be reported as an AE.

When the following EKG change conditions are met, study treatment **MUST** be discontinued, the study PI informed, and further steps discussed:

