9.4.4 Clinical Safety Laboratory Assessments

- Refer to [Appendix 2](#) for the list of clinical laboratory tests to be performed and to the SOA for the timing and frequency.
- The Investigator must review the laboratory report, document this review, and record any clinically relevant changes occurring during the study in the AE section of the CRF. The laboratory reports must be filed with the source documents. Clinically significant abnormal laboratory findings are those that are not associated with the underlying disease, unless judged by the Investigator to be more severe than expected for the participant's condition.

- All laboratory tests with values considered clinically significantly abnormal during participation in the study should be repeated until the values return to normal or baseline, with a frequency based on the judgement of the Investigator. If such values do not return to normal/baseline within a period of time judged reasonable by the Investigator, the etiology should be identified and recorded in the CRF.

The monitoring schedule proposed for a case of acute liver function abnormalities or worsening of a liver function abnormality is reported is listed in [Section 8.1](#) (Liver Test Abnormalities).

- Clinically significant liver function abnormalities should be reported as an AE/AESI.
- All protocol-required laboratory assessments, as defined in [Appendix 2](#), must be conducted in accordance with the SoA.

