APPENDIX 2: CLINICAL LABORATORY TESTS

- The tests detailed in the table below will be performed by the local laboratory.
- Protocol-specific requirements for inclusion or exclusion of participants are detailed in [Section 6.1](#) or [Section 6.2](#), respectively.
- Additional tests may be performed at any time during the study as determined necessary by the Investigator or required by local regulations.

Protocol-Required Safety and Efficacy Laboratory Assessments

Laboratory Assessments	Parameters			
Hematology	Platelet Count RBC Count Hemoglobin	Mean Cell Volume Mean Cell Hemoglobin	WBC count with differential (% and absolute counts): Neutrophils Lymphocytes Monocytes Eosinophils Basophils	International normalized ratio (INR)
Clinical Chemistry ¹	Blood urea nitrogen	Potassium	AST/Serum glutamic-oxaloacetic transaminase	Total bilirubin
	Creatinine	Sodium	ALT/Serum glutamic-pyruvic transaminase	Total protein
	Alkaline phosphatase	CPK		
Efficacy Biomarkers	Cell-free DNA Citrullinated histone H3 Myeloperoxidase (MPO)-DNA complexes	IL-1 beta IL-6 IL-8 TNF-alpha	Desmosine C-Reactive Protein	D-Dimer Fibrinogen Procalcitonin
PK	Pre or 1-2 hrs Post dose			
Other Screening and in Study Tests	
 Urine pregnancy test during the study (as needed for women of childbearing potential) Serum human chorionic gonadotropin pregnancy test (as needed for women of childbearing potential) All study-required laboratory assessments will be performed at the local laboratory, with the exceptions of the biomarker efficacy (see Section 9.2) and PK samples which will be sent to a central laboratory for curation and analysis. The results of each test must be entered into the CRF 			
¹ Details of liver chemistry stopping criteria and required actions and follow-up assessments after liver stopping or monitoring event are given in Section 8.1 . All events of ALT $\geq 3 \times$ ULN and bilirubin $\geq 2 \times$ ULN ($>35\%$ direct bilirubin) or ALT $\geq 3 \times$ ULN and INR >1.5 , if INR is measured, which may indicate severe liver injury (possible Hy's Law), must be reported as an SAE. ² Local urine testing will be standard.				

Investigators must document their review of each laboratory safety report.

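### One mandatory liver stop and the bilirubin limb of the possible Hy's-law SAE rule need direct bilirubin, which is in no list of required tests

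*Protocol*

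**What the plan says.** The rules:

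- Protocol Section 8.1 (Liver Test Abnormalities), item 3, opens "When the following abnormal liver test conditions are met" and makes discontinuation compulsory. Its last condition is "Alkaline phosphatase >2x ULN and direct bilirubin >2 x ULN".
- Appendix 2, footnote 1, refers back to Section 8.1 for the stopping criteria ("Details of liver chemistry stopping criteria and required actions and follow-up assessments after liver stopping or monitoring event are given in" that section). It then describes events "which may indicate severe liver injury (possible Hy's Law), must be reported as an SAE". One limb is ALT at or above 3x ULN with bilirubin at or above 2x ULN, qualified by more than 35% direct bilirubin. The other is ALT at or above 3x ULN with INR above 1.5.

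The tests:

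- Section 9.4.4 makes Appendix 2 the definition of the required set ("All protocol-required laboratory assessments, as defined in" that appendix) and ties it to the Schedule of Assessments.
- The only bilirubin entry in the Appendix 2 chemistry panel is "Total bilirubin". ALP, ALT and AST are in the chemistry panel, and INR is listed under hematology.
- Section 8.1, item 1, gives a repeat panel of ALT, AST, ALP and total bilirubin, and a close-observation panel of the same four: "Regular monitoring (twice to three times a week) is required (AST, ALT, ALP and TB)".
- The Schedule of Assessments shows generic safety blood draws. The SAP does not mention direct bilirubin.

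**The concern.** A compulsory stop should be decidable from data that the plan obliges the site to collect. Here the rule names one analyte and the panels name another. Two patients with the same liver picture could be handled differently, depending on whether someone ordered a test that the protocol does not list.

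Liver abnormality is one of the adverse events of special interest in the primary endpoint, and Section 5.8 relies on monitoring and discontinuation criteria to keep the liver risk manageable. Section 6.2, criterion 3, also admits patients with documented Gilbert's syndrome and total bilirubin below 5x ULN. Their total bilirubin can already lie above the 2x and 2.5x limits at entry, so rules on total bilirubin discriminate poorly for them and the direct fraction carries more of the information.

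**Working it through.** There is no stated figure to reproduce. The check sets each rule against the tests required.

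**1. Inputs of the liver rules against the required panel**

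| Rule | Place in protocol | Decidable from required tests? |
|---|---|---|
| ALT or AST ≥5x ULN, confirmed on repeat | 8.1 item 2 | Yes |
| ALT or AST >3x ULN with total bilirubin >2x ULN | 8.1 item 3 | Yes |
| ALT or AST >3x ULN with INR >1.5 | 8.1 item 3 | Yes |
| ALT or AST >ULN with clinical hepatitis | 8.1 item 3 | Yes |
| ALP >2x ULN with direct bilirubin >2x ULN | 8.1 item 3 | **No** |
| Raised bilirubin with symptoms or signs | 8.1 item 4 | Yes |
| INR ≥1.5 with total bilirubin ≥2.5x ULN | 8.1 item 4 | Yes |
| Total bilirubin and ALP both ≥2.5x ULN | 8.1 item 4 | Yes |
| SAE rule, bilirubin limb (>35% direct) | Appendix 2, footnote 1 | **Direct fraction: no** |
| SAE rule, INR limb | Appendix 2, footnote 1 | Yes |
| Liver AESI criteria | 9.5.3 | Yes |

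Direct bilirubin is used by 2 rules and listed in 0 of the 3 enumerated panels.

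**2. Can total bilirubin stand in?** Only in one direction. Direct bilirubin is part of total bilirubin, so direct ≤ total. The item 3 condition can be ruled out when ALP is at most 2x ULN, or when total bilirubin is at most 2 × the direct ULN. Otherwise it is undetermined. It can never be shown to be met.

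As an illustration, assume ULNs (not given in the documents) of 0.2–0.4 mg/dL for direct and 1.0–1.3 mg/dL for total bilirubin:

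- item 3 limit: 2 × 0.2–0.4 = 0.4–0.8 mg/dL direct bilirubin;
- item 4 limit: 2.5 × 1.0–1.3 = 2.5–3.25 mg/dL total bilirubin.

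On these assumptions the item 3 bilirubin limit can be reached with total bilirubin still within its normal range. The item 4 rule is therefore not a substitute.

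**3. Who falls in the gap?** A patient with ALP and direct bilirubin both above 2x ULN who meets no other row of the table. Against the item 4 cholestatic rule this means either ALP between 2x and 2.5x ULN, or ALP at or above 2.5x ULN with total bilirubin below 2.5x ULN. The transaminase and INR rules, and those needing symptoms or signs, must also be unmet.

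**4. What is lost in the SAE rule?** ALT above 3x ULN with total bilirubin above 2x ULN is already a mandatory stop (8.1 item 3) and an AESI reportable within 24 hours (9.5.3). Neither uses a direct fraction. Apart from values exactly on a limit (the footnote uses ≥, the other two use >), only the classification as an SAE is left open.

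**5. When could it matter?** In the 5-day schedule the safety draws are at screening, Day 1, Day 5 and Day 10. Day 5 is the end of treatment, so the first scheduled post-baseline draw cannot shorten a 5-day course. It can inform the decision to extend. The extension schedule has safety draws in Days 6 to 9 and on Day 10, while dosing continues: 5 days × 2 doses = at most 10 doses.

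**The case against.** The best defence is that the site has other routes to the result. Section 8.1 calls for a complete liver profile within 48–72 hours of a first abnormal value, Appendix 2 allows further tests at the investigator's discretion, and routine-care results may be used. The rule is also conjunctive: anyone who meets it has ALP above 2x ULN, which is on the panel and should prompt an investigator to ask for the direct fraction. Investigators must stop treatment for significant safety issues and may suspend it for important laboratory abnormalities. Section 10.3.1 tabulates out-of-range laboratory values.

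Much of this stands, and it limits the consequence. It does not close the gap. Apart from PT/INR, the contents of the complete liver profile are undefined. It is also attached to the listed scenarios, and this scenario cannot be recognised until direct bilirubin has been measured. A discretionary test cannot support a compulsory rule. The item 1 panels are triggered by ALT or AST, so an ALP-led change does not reach them. The AESI definition in Section 9.5.3 has no ALP or direct-bilirubin criterion, although clinically significant liver abnormalities are reportable under Sections 8.1 and 9.4.4.

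A reader might infer that liver monitoring as a whole fails, that possible Hy's-law cases would go unreported, or that a cholestatic change would pass unstopped and uncounted. The documents do not support any of these. The INR limb and every other liver stop work, the core Hy's-law pattern is stopped and expedited on total bilirubin, and a raised ALP is visible and tabulated.

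**Conclusion.** The point holds in a narrow form. The ALP/direct-bilirubin stop and the bilirubin limb of the possible Hy's-law SAE rule cannot be confirmed from the protocol-required tests. The practical exposure is an ALP-led cholestatic change below the item 4 thresholds, mainly at the Day 5 extension decision and over Days 6 to 10.

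Few such events are likely among 15 patients: Section 5.8 describes raised ALP and total bilirubin as uncommon in COVID-19, and the liver signal it reports for the drug is in transaminases. The documents give no rate from which to compute an expected number.

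The conclusion rests on Appendix 2 being the full required list, as Section 9.4.4 says. The Manual of Procedures was not available. If it already requires direct bilirubin, the remaining defect is one of protocol wording. The mg/dL illustration depends on assumed ULNs, and the finding does not need it. Severity: should-fix.

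**What to change.** Reconcile Section 8.1 (items 1, 3 and 4) with Appendix 2 (chemistry panel and footnote 1), so that the analytes collected are those the rules use. If the sponsor keeps the rules as written, one way is to:

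- list direct bilirubin in the Appendix 2 clinical chemistry panel, measured on the existing safety draws;
- add it to the repeat and close-observation panels in Section 8.1, item 1 (doing only this would miss an ALP-led change);
- state what the complete liver profile contains.

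Whether to align the panels to the rules or the rules to the panels is for the sponsor to decide. No change to any threshold, trigger or clinical rule is proposed here.

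Cost: protocol and laboratory-manual wording, a place for the result in the CRF, and one extra analyte on an existing tube for 15 patients. No extra visit or blood draw is needed.

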8.1.1 Temporary Discontinuation

Study treatment dosing may be temporarily suspended in the event of:

- Clinically important laboratory abnormalities
- Other intercurrent illnesses including acute new infection, major surgery, or gastrointestinal problems
- Use of prohibited treatment
- Any other protocol deviation that results in a significant risk to the participant's safety.

After a laboratory abnormality leading to a delay of dosing normalizes sufficiently, study treatment may resume at the discretion of the Investigator in consultation with the PI as needed. Similarly, study treatment may resume after the medication leading to suspension of dosing is discontinued. A decision to discontinue study treatment and/or to reinstitute study treatment should be conveyed to the Study PI. The Investigator may suspend study treatment at any time, without consultation with the Study PI if the urgency of the situation requires immediate action and if this is determined to be in the participant's best interest. However, the Study PI should be contacted as soon as possible in any case of study treatment discontinuation.

8.1.2 Dose De-escalation due to Study Drug Intolerance

If a participant is unable to tolerate study drug at any time during the study due to symptoms of headache, nausea or vomiting despite use of appropriate symptomatic or prophylactic treatments, the study drug dose may be reduced for the remainder of the treatment period. This may only occur if the following criteria are met and the event is considered related to study drug as assessed by the investigator:

- Adverse event of headache meeting Common Terminology Criteria for Adverse Events of \geq Grade 3 (Severe pain; limiting self-care activities of daily living).

And/or

- Adverse event of nausea meeting Common Terminology Criteria for Adverse Event of \geq Grade 3 (inadequate oral caloric or fluid intake).

And/or

- Adverse event of vomiting meeting Common Terminology Criteria for Adverse Event of \geq Grade 3 (requiring IV hydration or other medical intervention).

The change needs to be recorded in the CRF.

Refer to [Appendix 7](#) for further details of Common Terminology Criteria for Adverse Events (CTCAE).

8.1.3 Re-challenge

Resumption of study treatment after temporary discontinuation should always be discussed with the study PI or delegate.

Re-challenge should be performed one time only if the study medication was held due to AST or ALT ≥ 5 x ULN. Re-challenge should only occur after the ALT or AST return to pretreatment baseline value AND where there is a documented rationale that the elevation was not due to liver damage (e.g. technical error in blood test not compatible with the clinical picture and not present

on repeat testing, raised transaminase from muscle source supported by creatine phosphokinase results).

In the specific case of liver tests meeting the study treatment discontinuation criteria in [Section 8.1](#), no re-challenge is permitted.

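### After a mandatory liver stop, Protocol Section 8.1 conditionally allows restart while Section 8.1.3 rules out re-challenge, and neither says that it overrides the other

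*Protocol*

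**What the plan says.** **Protocol Section 8.1, Liver Test Abnormalities.**

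- Item 2 covers ALT or AST at or above 5 × ULN. If a repeat within 24 to 48 hours confirms it, "the drug should be discontinued and the patient followed until the laboratory values normalize or stabilize".
- Items 3 and 4 are the mandatory stops. Item 3 includes ALT or AST above 3 × ULN with total bilirubin above 2 × ULN or INR above 1.5, and a clinical-hepatitis criterion: "Any elevation in ALT or AST with clinical hepatitis: ALT or AST >ULN and the appearance of worsening fatigue", or one of several other listed signs. Item 4 includes two purely laboratory criteria (INR with total bilirubin; total bilirubin with alkaline phosphatase). Under both items the drug is stopped, "the study PI be informed, and further steps discussed".
- The paragraph after item 4 begins: "For each scenario, initiate potential DILI evaluation for alternative etiologies and consider a hepatology consult". It goes on: "Study medication can be restarted only if an alternative etiology is" definitively "identified and liver tests have returned to baseline".

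**Protocol Section 8.1.3, Re-challenge.** The section opens with resumption of treatment, which is always to be discussed with the study PI or a delegate. It then makes one allowance: "Re-challenge should be performed one time only if the study medication was held due to AST or ALT" at or above 5 × ULN. The conditions are return to the pretreatment value and a documented reason why the rise was not liver damage; a muscle source supported by creatine phosphokinase is one of its examples. It closes with a bar: "In the specific case of liver tests meeting the study treatment discontinuation criteria in" Section 8.1, no re-challenge is allowed. No exception is attached.

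The SAP contains no restart rule, and the protocol's summary of changes does not mention one.

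**The concern.** A hepatic stopping rule should give one answer before it is needed. Here a patient stopped under item 3 or 4, with another cause established and tests back at baseline, may resume under Section 8.1 and may not under Section 8.1.3. The stops in question include ALT above 3 × ULN with raised bilirubin or INR, which is essentially the pattern that the footnote to Appendix 2 treats as possible Hy's Law and requires to be reported as an SAE. Liver function abnormality is also an adverse event of special interest (Section 9.5.3). An investigator who follows Section 8.1 as written would breach Section 8.1.3 and re-expose a patient whom the second rule is meant to protect.

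**Working it through.** No figure in the plan depends on this point, so the check sets the two sections side by side and then works out how much dosing time could be left for a restart.

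**1. The rules, case by case**

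| Situation | Section 8.1 | Section 8.1.3 | Result |
|---|---|---|---|
| Item 3 or 4 stop; no definite other cause, or tests not at baseline | No restart | No re-challenge | Agree |
| Item 3 or 4 stop; other cause definite and tests at baseline | Restart allowed | No re-challenge | Opposite |
| ALT/AST ≥ 5 × ULN, drug held, not confirmed on repeat | Item 2 stop not triggered | One re-challenge, on conditions | Compatible |
| ALT/AST ≥ 5 × ULN confirmed on repeat; muscle source documented; back at baseline | Item 2 stop | The single re-challenge and the closing bar can both be read to apply | Unclear |

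**2. Readings that might reconcile the second row**

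- *Restart and re-challenge are different acts.* Section 8.1.3 itself begins with resumption of treatment, and the protocol defines no difference.
- *The restart sentence covers only item 4 and the bar only item 3.* The paragraph is expressly for each scenario, and two of the item 4 criteria are liver tests in the plain sense.
- *Section 8.1.1 decides.* It leaves resumption after a laboratory abnormality to the investigator, consulting the PI as needed. It does not say which of the other two rules governs.

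**3. How many patients could be re-exposed**

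Section 5.2 puts 10 of 15 patients on alvelestat. (SAP Table 1 has 7 to 8 per arm, so 10 is the ceiling under either document.) This is a ceiling and not an estimate; the documents give no rate for the event.

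**4. Whether any dosing time is left**

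Inputs: the safety-blood rows of the two Schedules of Assessments, and the Section 8.1 requirement to repeat the full liver profile 48 to 72 hours after the first abnormal value. Formula: days left after the recheck = last dosing day − (day of draw + 2 or 3). This assumes that baseline has been regained and the cause established by that first recheck, which is the most favorable case for a restart.

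- 5-day course: the only scheduled safety draw after baseline and during dosing is Day 5, the last dosing day. Dosing days left at the draw: 5 − 5 = 0.
- Day 5 draw in a patient going on to the extension: recheck Day 7 to 8; 10 − 7 = 3, 10 − 8 = 2.
- Day 6 draw in the extension: recheck Day 8 to 9; 10 − 8 = 2, 10 − 9 = 1.
- Day 7 draw: recheck Day 9 to 10; 1 to 0 days left. A Day 8 or later draw leaves none.
- Illustrative routine-care draw on Day 2 (the Schedule allows routine-care results to be used): recheck Day 4 to 5; 1 to 0 days left in a 5-day course, or 6 to 5 if the course is extended to Day 10.

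Scheduled draws therefore leave at most about 3 days, and only in the extension. Anything longer needs an early abnormal routine-care result and an extended course.

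**The case against.** The strongest reply is that the two texts can be lived with. The restart sentence in Section 8.1 says only-if, which sets necessary conditions and grants no entitlement. Section 8.1.3 is the dedicated section, presents its bar as a specific case and is stricter. An investigator who never restarts breaks neither rule. The study is single-center and the PI must be informed in any event.

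Much of this stands. No breach is forced, and a safe course exists. But if only-if is read as a bare condition, the restart sentence has almost nothing left to do, and a reader will naturally take it as permission. Involving the PI does not tell the PI which rule governs.

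Four stronger readings are tempting, and the documents do not support them:

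- A reader might infer that the two sections ignore each other. They do not: Section 8.1.3 refers expressly to the Section 8.1 criteria. What is missing is a statement of precedence.
- A reader might infer that the conflict arises readily in patients who enter with transaminases already somewhat above ULN and then become febrile. The liver block opens for acute or worsening abnormalities, so an unchanged ALT may not enter it at all.
- A reader might infer that different sites would apply different rules. There is one center.
- A reader might infer that re-challenge should be barred after every confirmed rise to 5 × ULN or more. That would largely empty the muscle-source example which Section 8.1.3 offers, since a true muscle-source rise may well persist at a 24 to 48 hour repeat. It would be a new clinical policy and not a repair.

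**Conclusion.** The inconsistency is real in the current text and should be corrected. After an item 3 or 4 stop, Section 8.1 conditionally permits restart and Section 8.1.3 forbids it, with no stated precedence. Separately, Section 8.1.3 does not settle a confirmed ALT or AST at or above 5 × ULN with a documented muscle source.

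The size is small. At most 10 patients could be re-exposed to active drug. Each would have to meet a stop, have another cause definitively shown and regain baseline while doses remain, which is realistic only from routine-care bloods or in the Day 6 to 10 extension. No sample size, error rate or analysis is affected. The conclusion rests on reading restart and re-challenge as the same act, and on taking the paragraph after item 4 to apply to items 3 and 4 alike. The judgment that it will be rare rests on the visit schedule and not on an observed event rate.

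**What to change.** In Protocol Section 8.1, replace the restart sentence with:

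> *Study medication must not be restarted after a stop under items 3 or 4; for a hold or stop for ALT or AST ≥5 × ULN, see Section 8.1.3.*

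In Section 8.1.3, replace the last sentence with:

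> *No re-challenge is permitted after a stop under Section 8.1 liver items 3 or 4. The single re-challenge above applies only to a hold or stop for ALT or AST ≥5 × ULN (item 2) with return to pretreatment baseline and a documented non-hepatic cause.*

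This keeps the stricter rule for the mandatory stops and leaves the muscle-source allowance in place. The SAP needs no change. The cost is two reworded sentences in the protocol and, for a rare patient with a proven alternative cause, the loss of a few dosing days.
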